A feasibility study undertaken by the chief investigator (CI), as part of a PhD programme of study, determined that an ankle placement of the Actigraph GT3X accelerometer was superior to the waist for determination of body position and step count. In this study, thirty healthy adult volunteers simulated patients weakened by critical illness. They performed a movement protocol which incorporated the typical activities undertaken by patients recovering in hospital from critical illness. These included moving from lying to sitting, sitting to standing (and vice versa) and walking short distances. Video recordings were taken of each participant during the movement protocols, enabling observation of the body positions adopted and step counting during the walking activities. Video recording was used as the criterion measure for comparison against the data captured by the accelerometers worn both at the ankle and the waist. The activities detailed above are typically included within early mobility protocols which have undergone evaluation within populations experiencing critical illness (McWilliams et al., 2015, Adler and Malone, 2012, Schweickert et al., 2009). Moderate agreement ($\kappa = 0.43$, $p < 0.001$), was found between observation of video recordings of body position (lying, sitting or standing) and the inclinometer setting for the ankle placement. Fair agreement only ($\kappa = 0.21$, $p < 0.001$) was found for the waist placement. Regular misclassification of all body positions was found with the waist placement. The ankle placement identified both the lying and standing positions well. The sitting position however was only correctly identified intermittently for the ankle placement. A novel finding emerged from this research relating to the ankle placement site. When a side lying position was adopted, the ankle accelerometer inclinometer function regularly registered a '0'. The '0' setting normally corresponds to a 'not being worn' option. When a reading of '0' was recoded to the option 'side lying,' agreement improved from $\kappa = 0.43$ ($p < 0.001$) to $\kappa = 0.48$ ($p < 0.001$). This finding suggests a new way of interpreting the '0' reading of the inclinometer when worn on the ankle, which is worthy of further investigation within an actual patient population.

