The inconsistency of correct determination of body position of this accelerometer model when worn around the waist has been demonstrated by other authors (Berendsen et al., 2014, Hänggi et al., 2013). The inconsistency of correct identification of the sitting position in particular was highlighted by (Hänggi et al., 2013). Other researchers have investigated ways of improving the ability to correctly classify the sitting position (Skotte et al., 2014). The study by (Skotte et al., 2014)

determined that the addition of a second Actigraph GT3X accelerometer placed on the mid-thigh yielded excellent results in detection of the sitting position. Pressure sensors in subjects' hip pockets were used as a criterion measure to classify body position.

As mentioned previously, the feasibility undertaken by the CI determined that the ankle placement was superior to the waist for recognition of step count. When walking a ten metre distance with a walking aid, using observed step count as a criterion measure the ankle placement demonstrated a mean difference -1 step, (Limits of Agreement (LOA) +3 to -5 steps) compared to the waist placement (mean difference -7 steps, LOA +9 to -23 steps). These positive findings for step count for the ankle placement are supported by a recent study cited earlier using a similar Actigraph model investigating the accuracy of step count in older adults (Korpan et al., 2015).

Defining the research question

Using the findings from the feasibility study regarding the ankle placement of the Actigraph GT3X accelerometer and the research cited suggesting improved classification of the sitting position with the addition of a thigh mounted accelerometer the following research question is proposed:

Can an Actigraph GT3X accelerometer, placed at the ankle and thigh of the same leg, accurately measure body position and walking episodes undertaken by patients recovering from critical illness in a hospital ward?

A number of study objectives evolve from this research question, assisting in the development of the methodological processes required to answer it.

1. To determine the criterion validity of the ActiGraph GT3X accelerometer in detection of body position and step count when positioned either on the mid-thigh or ankle of the same leg.
2. To establish if there is a superior single body placement site (thigh or ankle) to objectively record body position and step count within this patient population.

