3. To investigate the criterion validity of the combination of thigh and ankle accelerometer inclinometer outputs to correctly determine the sitting position. This

will determine whether an algorithm can be constructed using the two inclinometer readings, which will better distinguish the sitting from the standing position.

4. To evaluate, from a user perspective, the acceptability of these devices in relation to the placement sites used. This will be achieved by asking patients to score the answer to a particular question through the use of a Likert scale. The question is:
 - How would you rate the comfort of wearing the accelerometers?

In consideration of the results from the feasibility study undertaken by the CI and research using the addition of a thigh mounted accelerometer to identify the sitting position (Skotte et al., 2014), the following hypotheses can be constructed:

Hypotheses

1. An ankle mounted Actigraph GT3X accelerometer, will accurately identify both the lying and standing positions when compared with direct observation as a criterion measure.
2. An ankle mounted Actigraph GT3X accelerometer, will capture a step count comparable to that recorded by direct observation in a population resident on a hospital ward recovering from critical illness.
3. The combination of inclinometer outputs of both the thigh and ankle placement sites will permit development of an algorithm permitting the ability to better distinguish between the sitting and standing position.
4. The ankle and mid-thigh accelerometer placement sites will be well tolerated by patients recovering on a ward from critical illness.

Subject selection and involvement

The study will invite adult hospital ward patients recovering from critical illness to wear one Actigraph GT3X accelerometer on the antero-medial mid-thigh and another on the ankle, resting above the lateral malleolus of the same leg. The accelerometers will be worn for a period of time not exceeding three hours. Each device will be attached with a single patient use broad elastic belt, secured by Velcro fastening, using a standardised placement protocol. The non – dominant leg will be the preferred placement side.

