A sample size of 20 participants will be recruited. This sample size has been used in previous research investigating the validity of a different accelerometer model to quantify gait parameters in patients recovering from critical illness (Edbrooke et al., 2012). They predicted that 12 subjects were necessary based upon alpha = 0.05 (significance level), beta = 0.9 (power) and a correlation of $r = 0.75$, categorised as a good to excellent correlation (Trapp and Dawson, 2004). A sample size of 20 was also recruited in another study investigating the validity of accelerometer measurement within a hospitalised stroke population (Kramer et al., 2013). Recruiting a sample of 20 patients will permit some attrition should there be any accelerometer malfunction or decisions to withdraw, yet supply an achievable number for participant recruitment based on feedback from clinical colleagues working within the specialty.

Statistical analysis

IBM SPSS statistics (Version 20) will be used to undertake statistical analysis. Some data captured by the accelerometers is continuous and others categorical.

Categorical data

Categorical data, concerning body position (lying, sitting or standing) will be analysed using the Kappa statistic, calculating agreement between the accelerometer inclinometer data and direct observation. Each accelerometer placement site (thigh and ankle) will initially be analysed separately. Examination of the inclinometer raw data captured from both placement sites will determine whether an algorithm can be constructed using readings from both the ankle and thigh placement to improve determination of the sitting

position specifically if necessary. Direct observation will serve as the criterion measure for all the analyses.

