Percentage agreement of inclinometer raw data from the thigh and ankle accelerometers with direct observation for detection of each separate body position will be calculated. A further percentage agreement analysis will be undertaken if an algorithm can be constructed for determination of the sitting position using readings from both placement sites. This algorithm will be compared against direct observational raw data identifying the sitting position only. This result will be compared against the percentage agreement of the individual placement sites in determination of the sitting position. This will assist in determination of whether the algorithm is more superior to a single placement site in determination of the sitting position.

Continuous data

Agreement between step count recorded by each accelerometer placement site and direct observation (manual counts) as a criterion measure will be determined using Bland Altman analysis with 95% limits of agreement (LOA).

Acceptance of the devices over a three-hour period

The statements within the Likert scale will be collapsed to obtain true positives (very comfortable and somewhat comfortable) and true negatives (very uncomfortable and somewhat uncomfortable). The middle category (neither comfortable nor uncomfortable) will remain a separate category. A descriptive analysis will be undertaken to investigate this particular aspect of enquiry using percentages of true positives, the middle category and true negatives. This will be presented graphically.

Any specific comments made by the patients in relation to acceptability of the devices will be included as free text within the results section. The statements will be anonymous and permission from participants will be sought regarding their inclusion within the body of the thesis or publications which may arise from it.

Ethics approval

This study has received approval from the NHS Local Research Ethics Committee (REF: XXXXX) and the Research Ethics Sub Committee, YSJU (REF: XXXXXX).

Data handling and confidentiality

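### Step count is to be judged by limits of agreement from at most 20 people, with no confidence interval stated and no acceptable error fixed in advance, so Hypothesis 2 has no prespecified criterion.

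*Combined protocol and SAP*

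**What the plan says.** The step-count analysis is one sentence, under Statistical analysis, Continuous data: agreement between each placement site and manual counts "will be determined using Bland Altman analysis with 95% limits of agreement (LOA"). Hypothesis 2 states that the ankle device "will capture a step count comparable to that recorded by direct observation". No number is attached to either statement.

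Under Sample size calculation, "A sample size of 20 participants will be recruited", and attrition comes out of that number: "Recruiting a sample of 20 patients will permit some attrition should there be any accelerometer malfunction or decisions to withdraw". The one calculation cited there belongs to another study of a different accelerometer: "They predicted that 12 subjects were necessary", from "alpha = 0.05 (significance level), beta = 0.9 (power") and a correlation of 0.75.

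The background gives the feasibility result for the ankle over ten metres with a walking aid: "mean difference -1 step, (Limits of Agreement (LOA) +3 to -5 steps"). It calls the ankle findings positive but does not adopt them as a benchmark, and it quotes them without intervals. The volunteers were 30 healthy adults simulating weakness.

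Study procedure gives all data collection and the statistical analysis to the chief investigator. It lists times, type of movement, body position and step count as recorded, and does not list distance. The movement protocol lets each participant's ability set the walking distance.

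**The concern.** Limits of agreement describe how far the device departs from the observer. They do not say whether that departure is tolerable. Someone has to state the tolerable error, and the statement has force only if it is made before the limits are known. Here the person who counts the steps and runs the analysis would also decide afterwards what *comparable* means.

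The second issue is precision. Limits estimated from 20 people or fewer are uncertain, and the uncertainty matters because the device is proposed as a clinical measurement tool. The error that can occur in a single patient is therefore the figure a ward would rely on. Limits given without intervals would make that error look better known than it is.

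**Working it through.** **The cited sample size.** Testing a correlation of zero against 0.75 by Fisher's z, one-sided: ((1.645 + 1.282)/0.973)² + 3 = 12.05. A simulated t-test of the correlation gives power 0.924 at n = 12 and 0.899 at n = 11, so 12 is reproduced one-sided. Two-sided, the formula gives 14.10. Either way the figure concerns a correlation, which is not the planned step-count analysis, and it says nothing about the precision of limits of agreement.

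**Assumptions from here on.** Differences are normal and each participant contributes one difference. n = 20 is the planned maximum.

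**Precision in SD units.**
- Exact 95% bounds for a limit: k = q/√n, where q is the 0.025 or 0.975 quantile of a non-central t with 19 df and non-centrality 1.96 × √20 = 8.765. This gives k = 1.357 and 3.014.
- Usual approximation: half-width = t × √(1/n + 1.96²/(2(n − 1))) = 2.093 × √(0.05 + 3.842/38) = 0.81 SD.
- Average share of future differences inside mean ± 1.96 SD: P(|t₁₉| < 1.96/√1.05) = P(|t₁₉| < 1.913) = 92.9%.

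**In steps, if the feasibility ankle SD carried over.** SD = 8/(2 × 1.96) = 2.04, mean -1.

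| Quantity | Estimate | 95% interval, n = 20 |
|---|---|---|
| Bias | -1 | -1 ± 2.093 × 2.04/√20 = -1.96 to -0.04 |
| Lower limit (exact) | -5 | -1 − 3.014 × 2.04 to -1 − 1.357 × 2.04 = -7.2 to -3.8 |
| Upper limit (exact) | +3 | -1 + 1.357 × 2.04 to -1 + 3.014 × 2.04 = +1.8 to +5.2 |

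The approximation gives -6.7 to -3.3 and +1.3 to +4.7.

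**Range.** At n = 16 the exact outer bounds widen to -7.5 and +5.5. If variability were like the feasibility waist placement (limits +9 to -23, so SD = 32/3.92 = 8.16, mean -7), the exact intervals at n = 20 would be -31.6 to -18.1 and +4.1 to +17.6.

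**What margin could n = 20 meet?** I simulated 2,000,000 studies of 20 with true mean -1 and SD 2.04, and counted those in which both outer exact bounds fell inside a given range.

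| Range (steps) | Half-width in SD | Studies passing |
|---|---|---|
| -7 to +5 | 6/2.04 = 2.94 | about 35% |
| -8 to +6 | 7/2.04 = 3.43 | about 71% |
| -9 to +7 | 8/2.04 = 3.92 | about 93% |

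The half-widths in SD units carry over to another scale, if differences are normal on it and the range is centred on the true bias. The documents give no step total for the ten-metre walk, so the ranges cannot be converted to percentages here.

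**The case against.** This is a small, unfunded, descriptive validation study within a PhD, and Bland-Altman limits are the standard description. A reader might infer that the plan means to report bare limits as if they were exact. The documents do not support that: they are silent on intervals and do not exclude them, and an analyst could add them. A reader might also infer that no result could count against Hypothesis 2. That is too strong. Limits like the feasibility waist result would look poor to anyone. What is missing is a criterion fixed beforehand.

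The conventional 1.96 multiplier is not an error either. The small-sample multiplier, 2.093 × √1.05 = 2.145, would move limits of -5 and +3 only to -5.4 and +3.4, and it is optional once intervals are reported.

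The step figures rest on a weak transfer from healthy volunteers on a fixed course to patients walking distances of their own choosing. That objection stands, and it is why the figures are given as an assumption with a range. It does not touch the results in SD units, nor the absence of a criterion.

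**Conclusion.** The point holds as a gap in prespecification. The plan neither defines *comparable* nor states how the uncertainty of the limits will enter the judgement, and the sample size section does not fill either gap. At n = 20 each limit is known only to lie between 1.36 and 3.01 SD from the mean, given normality and one difference per participant. In steps, under the feasibility ankle SD, an observed lower limit of -5 is compatible with a true one as far out as -7.2, and an observed upper limit of +3 with one as far out as +5.2.

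It would be a mistake to take roughly -7 to +5 from these intervals as a margin this study can be expected to meet. A device performing exactly as in feasibility would meet it in only about 35% of studies. The design remains usable, and the remedy is a cheap improvement to the text.

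**What to change.** Add to the Continuous data section, before the first participant:

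1. Report 95% confidence intervals for the bias and for both limits at each site, using the exact non-central t method for the limits.
2. State the largest acceptable step-count error as a percentage of observed steps. An absolute or per-distance error does not fit, because distance is self-chosen and is not listed as recorded.
3. Call Hypothesis 2 supported only if the outer confidence bounds of both ankle limits lie inside that error.
4. Take the margin from the intended use, then check it against what n = 20, less attrition, can show. If the margin is out of reach, say so in advance.
5. Say whether each participant contributes one walk or several. If several, the limits and their intervals must allow for repeated measures.

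The cost is a few sentences and a short calculation. No new data are needed, since the manual counts already supply the denominator. The reported uncertainty will be wider, the investigator commits to a margin, and percentages will be volatile for very short walks.
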